### **Reconsenting**

In the event that the consent is amended, participants who are active and have not yet completed the study will be informed of these changes and be asked to sign the updated consent form. The updated consent form will be provided to them at an upcoming visit, or through mail, email or fax. They will be given time to review these changes and provide their written consent. They may sign and return it to the research team at the upcoming visit, or through mail, email or fax.

Participants who have completed the study and are no longer active in the study will be made aware of the changes through mail, email or fax. However, these participants will not be asked to acknowledge or confirm the receipt of the updated consent or to sign and return it.

---

### 13. ALTERNATIVES TO STUDY PARTICIPATION

Subjects have the right to refuse participation in the study. Patients will have no changes to their current medical regimen. They can choose to withdraw at any time.

### 14. POTENTIAL RISKS

1. Ivabradine: Labeled side effects include: bradycardia, hypertension, atrial fibrillation, and visual distortions (visual brightness, diplopia, visual impairment, phosphenes).
2. Venipuncture: pain, a bruise at the point where the blood is taken, discoloration, redness and swelling of the vein and infection.
3. Tilt table test: Patient will lie flat on a table and straps will be secured. After 15 minutes, the table will be quickly tilted to raise the body to stimulate a change in position like standing. Patient will remain secured and in “standing” position for up to 45 minutes, while being monitored continuously. Only qualified medical professionals will perform this test. There may be an increased risk of prolonged hypotension or tachycardia when in “standing” position. These minor complications improve once the table is returned to the horizontal position.
4. Orthostatic heart rate monitoring: Only qualified medical professionals will perform this test. There may be an increased risk of hypotension or tachycardia upon changing positions from laying down to sitting to standing. Patient will be monitored to avoid such risks and treatment will be provided if necessary to return patient to resting heart rate.
5. Quality of life (QOL) questionnaire: Although there are no known adverse risks, some patients may experience frustration, stress, discomfort, fatigue and boredom. These risks will be addressed by informing participants in advance and allowing them to stop or pause the questionnaire at any time if they wish, and resume when they are ready.
6. Washout Period: The washout period may increase risks of cardiovascular events, such as tachycardia.
7. A potential loss of confidentiality: The UCSD Institutional Review Board (IRB), the FDA, and other government agencies may inspect the study records. To minimize the risk of a potential loss of confidentiality, subjects will be assigned a unique subject code and their blood samples will be assigned a different unique specimen code. A separate paper document will link patient identifiers with subject codes and specimen codes. This document will be kept in a secure location in a locked cabinet. Only the PI and study coordinator will have the key to the cabinet. No research documents will have any patient identifiers and will only be labeled with the unique assigned subject codes.
8. Unscheduled visits: There may be the possibility of having patients return for unscheduled visits in between the scheduled visits. This would be based on PI discretion and/or if the bloodwork needs to be redrawn due to lab or processing errors.

### 15. RISK MANAGEMENT PROCEDURES AND ADEQUACY OF RESOURCES

All subjects are screened with a medical history and physical exam to ensure none has health problems that put them at risk. Subjects will be thoroughly informed as to these potential problems.

Because this is a low risk study, a Data Safety Monitoring Board (DSMB) is not necessary. Instead, a Data Safety Monitoring Plan (DSMP) is provided.

**A DSMB is not needed for this study for various reasons:**

- The study meets the following IND exemption criteria: **The drug product is lawfully marketed in the United States, and the intent was to provide some latitude to modify the marketed version of the drug product for use in the clinical investigation (see attached Supplement to Biomedical Application Research Plan IND Exemption).**
- This is a low risk study assessing the impact of the drug on lowering heart rate in a specific patient population.
- The study does not involve a high-risk intervention or a vulnerable population, so DSMB should not be needed.
- This is a single site study that is **not intended** to evaluate treatments intended to prolong life or reduce risk of a major adverse health outcome.
- This study is **not intended** to compare rates of mortality or major morbidity.
- This study is addressing lesser outcomes, such as improving patient adherence
- The study population is not at an elevated risk of more severe outcomes.

## DATA SAFETY MONITORING PLAN (DSMP)

### Oversight responsibilities

Oversight of the trial is provided by the Principal Investigator (PI), [name].

### Monitoring procedures

[name] assures that informed consent is obtained prior to performing any research procedures, that all subjects meet eligibility criteria, and that the study is conducted according to the IRB-approved research plan. Study data are accessible at all times for the PI to review. The PI reviews study conduct such as accrual, drop-outs, protocol deviations on a monthly basis. The PI reviews AEs individually real-time and in aggregate on a weekly basis. The PI reviews serious adverse events (SAEs) in real-time. The PI ensures all protocol deviations, AEs, and SAEs are reported to the IRB according to the applicable regulatory requirements.

### Collection and reporting of SAEs and AEs

For this study, the following standard AE definitions are used:

**Adverse event:** Any unfavorable and unintended sign (including an abnormal laboratory finding), symptom or disease temporally associated with the use of a medical treatment or procedure, regardless of whether it is considered related to the medical treatment or procedure.

**Serious Adverse Event:** Any AE that results in any of the following outcomes:

- Death
- Life-threatening
- Event requiring inpatient hospitalization or prolongation of existing hospitalization
- Persistent or significant disability/incapacity

AEs are graded according to the following scale:

**Mild:** An experience that is transient, & requires no special treatment or intervention. The experience does not generally interfere with usual daily activities. This includes transient laboratory test alterations.

**Moderate:** An experience that is alleviated with simple therapeutic treatments. The experience impacts usual daily activities. Includes laboratory test alterations indicating injury, but without long-term risk.

**Severe:** An experience that requires therapeutic intervention. The experience interrupts usual daily activities. If hospitalization (or prolongation of hospitalization) is required for treatment it becomes an SAE.

The study uses the following AE attribution scale:

**Not related:** The AE is clearly not related to the study procedures (i.e., another cause of the event is most plausible and/or a clinically plausible temporal sequence is inconsistent with the onset of the event).

**Possibly related:** An event that follows a reasonable temporal sequence from the initiation of study procedures, but that could readily have been produced by a number of other factors.

**Related:** The AE is clearly related to the study procedures.

AEs are identified immediately after the study procedure. We will have the patient rest for 30 minutes to an hour after the procedure or activity to observe him or her for any AEs. We will follow up with patient the next day and once a week for the following weeks leading up to their next appointment with us. [name] who is a cardiologist and a team of nurses will always be nearby the patient at the appointment in case an event occurs.

SAEs and specific procedure-associated AEs are reported to the PI, IRB, and Amgen within 24 hours; PI will report to the FDA in a timely manner. In addition, all AEs are reported according to the IRB AE reporting guidelines.

If a patient becomes pregnant during the study or within a month after the study has ended, patient will be advised to inform the PI immediately and to inform her pregnancy doctor. Patient may be withdrawn from study if she becomes pregnant and the use of the drug will be discontinued. For pregnancies and lactation cases, the PI is responsible for asking the patient if they are willing to allow Amgen to collect pregnancy/birth outcome and/or breastfeeding information and the PI will provide patient's response to Amgen. The PI will be held responsible for reporting SAEs in a timely manner. The PI will attempt to assess any relationship between the procedures and adverse events to prevent future incidences.

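### The closed serious-event list means that a severe ivabradine reaction treated without admission, or a birth defect after exposure, can fall outside the 24-hour report

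*Combined protocol and SAP*

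**What the plan says.** All of this stands in section 15, Data Safety Monitoring Plan, under Collection and reporting of SAEs and AEs.

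- **Definition.** A serious adverse event is "Any AE that results in any of the following outcomes". The four entries are death, "Life-threatening", "Event requiring inpatient hospitalization or prolongation of existing hospitalization" and "Persistent or significant disability/incapacity". The list ends there.
- **Severity scale.** The top grade, Severe, is for events that need treatment and interrupt normal activities. On seriousness it adds: "If hospitalization (or prolongation of hospitalization) is required for treatment it becomes an SAE".
- **Attribution scale.** It is worded for procedures and does not name the drug. Its top category reads "The AE is clearly related to the study procedures".
- **Reporting.** "SAEs and specific procedure-associated AEs are reported to the PI, IRB, and Amgen within 24 hours". Reporting to the FDA is promised without a fixed time. For everything else, "all AEs are reported according to the IRB AE reporting guidelines".
- **Pregnancy.** A patient who becomes pregnant during the study or within a month of its end is advised to tell the investigator at once, and the drug is discontinued. The investigator asks whether she will let the funder collect pregnancy and birth outcome data, and passes on her answer.

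**The concern.** The plan does without a data safety monitoring board, and oversight rests with the principal investigator. Prompt notice to anyone outside the study team therefore depends on what counts as serious. The plan itself lists bradycardia, hypertension and atrial fibrillation among the expected effects of ivabradine (section 14, and Expected AEs in section 15). It also requires highly effective contraception until one month after the drug is stopped (sections 10 and 11), so it regards exposure in pregnancy as a risk. If such events can be severe, or can harm a pregnancy, without meeting the definition, then the IRB and the funder may hear of them later than a reader of the 24-hour rule would expect.

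**Working it through.** No arithmetic applies. The check follows an event from the definition to the reporting rule and looks for any other route that would catch it.

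**1. Is the list closed?** Yes. It is a definition by named outcomes with four entries. No other section adds an entry for events that needed intervention to prevent one of those outcomes, or for congenital anomaly.

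**2. Does a Severe grade make an event serious?** Not by itself. The severity scale names one route from Severe to serious, which is hospitalization. The life-threatening and disability entries still apply in their own right, with or without admission.

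**3. Does the second 24-hour class cover drug reactions?** The class of specific procedure-associated events is never defined, and the text points both ways.
- Against coverage: the definition of an adverse event names treatment and procedure separately, and the reporting sentence uses only the second word.
- For coverage: the attribution scale classifies every event by its relation to study procedures, and Expected AEs lists taking ivabradine beside the blood draw and the tilt test. That list also includes the washout period, however, so it is not strictly a list of procedures.

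Coverage of drug reactions is therefore ambiguous. It is neither stated nor excluded.

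**4. Can admission be taken for granted?** No. AE Management says that for an event during an appointment, staff give immediate care and send the patient to hospital; it does not say that the patient is admitted. For an event after the appointment it provides only for referral to medical care. Ivabradine is taken twice daily for a month with visits about two weeks apart (section 9), so drug reactions can also arise at home.

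**5. Does the pregnancy paragraph close the gap for birth defects?** No. It states no reporting time, collection depends on the patient's agreement, and it does not class an abnormal birth outcome as serious.

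**6. Cases traced through the text**

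| Event | Entry met | 24-hour report? |
|---|---|---|
| Severe bradycardia or atrial fibrillation, not life-threatening, treated without admission, no lasting disability | None | Only if read into the undefined procedure-associated class |
| Same event, judged life-threatening | Threat to life | Yes |
| Same event, patient admitted | Hospitalization | Yes |
| Birth defect after exposure | None explicit | No, unless read as disability or death; otherwise the pregnancy route, with no clock |
| Pregnancy complication that threatens life or leads to the mother's admission | Threat to life or hospitalization | Yes |

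The gap is rows one and four.

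**The case against.** The strongest reply is that the plan already catches the worst cases and that little is lost for the rest. Several parts of it stand.

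- A threat to life is a separate entry that needs no admission, so the most dangerous bradycardias and arrhythmias are serious as the text is written.
- For events at an appointment, the plan sends the patient on to hospital. It would be wrong to read it as planning treatment on site alone.
- A reader might infer that the 24-hour report is the only outside check. It is not: all adverse events go to the IRB under its guidelines, and Monitoring procedures has the investigator review each event in real time and report to the IRB as regulations require. Those guidelines are not in the documents and may set their own time limit.
- A reader might also infer that harm to a pregnancy goes unreported. The plan has a separate pregnancy route, and a maternal complication that threatens life or leads to admission is serious.

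A last objection is that the missing entries look like a defect only against an outside definition. The point does not need one. It rests on the plan's own rules: it grades an event as Severe, expects drug reactions and guards against exposure in pregnancy, yet its fast report does not clearly reach either case. None of the replies places the first and fourth cases in the table under the 24-hour rule.

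**Conclusion.** The gap is real but narrow. A severe, non-life-threatening ivabradine reaction treated without admission can miss the 24-hour report to the IRB and the funder. A birth defect after exposure is not classed as serious and has no reporting time. The stronger statement, that such events will miss the report, is not supported: life-threatening and admitted cases are covered, and the undefined procedure-associated class could be read to include drug reactions.

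The size cannot be computed, because the documents give no rates for these reactions or for treatment without admission. The crossover is planned for 20 patients, each due to take ivabradine for one month, so the absolute number should be small. For a non-admitted drug reaction, what is at stake is the stated 24-hour clock and the funder's copy, not whether the IRB ever hears of it.

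The conclusion assumes that the procedure-associated class is not meant to include drug reactions, or at least that staff could reasonably read it so. If it is meant to include them, that has to be written down, and the birth-defect gap remains in any case. Sample size, power and the primary analysis are unaffected. The change is worth making because it is cheap and because no monitoring board stands behind the investigator.

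**What to change.** In section 15, under Collection and reporting of SAEs and AEs:

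1. Add two entries to the list of serious outcomes: *congenital anomaly or birth defect*, and *other important medical event that, in the investigator's judgement, required intervention to prevent one of the above outcomes*.
2. Replace the undefined procedure-associated class with a statement that the 24-hour rule covers serious events and any event graded Severe that is associated with the study drug or a study procedure.
3. Give a reporting time for pregnancies and their outcomes. Patient agreement may still govern the collection of further birth data, but the text should say what is reported, to whom and by when.

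The cost is a protocol wording change and a few more expedited reports in a 20-patient trial.

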### **Management of risks to subjects**

#### *Expected AEs*

1. Blood draw
  - a. Hematoma
  - b. Arterial puncture
  - c. Pain
  - d. Nerve damage
  - e. Re-bleeding
  - f. Allergy
  - g. Phlebitis
  - h. Vasovagal reaction
  - i. Anxiety/fear
2. Tilt table test
  - a. Prolonged hypotension
  - b. Increased tachycardia
3. Orthostatic heart rate monitoring
  - a. Acute hypotension
  - b. Increased tachycardia
4. Consuming Ivabradine
  - a. Bradycardia

- b. Hypertension
  - c. Atrial fibrillation
  - d. Luminous phenomena (phosphenes)
5. Washout period
- a. Increased risk for cardiovascular events such as tachycardia

### AE Management

1. Blood Draw:
- a. Prior to enrollment into the study, the patient will be educated on the risks of the blood draw. The phlebotomist will calm the patient beforehand to reduce anxiety/fear and minimize the probability of vasovagal response. Only sterile needles and gauze will be used to prevent allergic reactions and infection. The area of the blood draw will be thoroughly sanitized with an alcohol wipe prior to the needle stick. Care will be used when penetrating the skin with the needle so that there is a minimized risk of punctured artery and damaged nerve. The needle stick will be done swiftly and securely by an experienced phlebotomist in order to reduce pain. Pressure will be applied on the area immediately after the needle stick to minimize the risk of hematoma. The phlebotomist will inform the patient on when and how to undress their puncture site. [name], who is a cardiologist, will be overseeing the procedure to check for the patient's vital signs. [name] phone number will be given to the patient for any questions or concerns that may arise in the future.
  - b. In the event of an AE that occurs during the appointment, the facility is equipped with trained medical staff (physicians and nurses) who can respond quickly. Should an event occur, [name] and the nurses will be nearby to administer immediate medical care and send the patient to the nearest hospital. If the AE occurs after the appointment, the patient will be referred for prompt medical attention. The patient will be withdrawn from the study. [name] will monitor the patient until the problem has been resolved or has stabilized.
2. Tilt table test:
- a. Prior to enrollment into the study, the patient will be educated on the risks of the tilt table test. The physician will calm the patient beforehand to reduce anxiety/fear and minimize the probability of vasovagal response. [name], who is a cardiologist, will be conducting and overseeing the procedure to check for the patient's vital signs. [name] phone number will be given to the patient for any questions or concerns that may arise in the future.
  - b. In the event of an AE that occurs during the appointment, the facility is equipped with trained medical staff (physicians and nurses) who can respond quickly. Should an event occur, [name] and the nurses will be nearby to administer immediate medical care and send the patient to the nearest hospital. If the AE occurs after the appointment, the patient will be referred for prompt medical attention. The patient will be withdrawn from the study. [name] will monitor the patient until the problem has been resolved or has stabilized.
3. Orthostatic heart rate monitoring:

- a. Prior to enrollment, the patient will be informed about the risks of orthostatic heart rate monitoring. The physician will comfort the patient to reduce anxiety/fear in order to minimize the probability of a vasovagal response. [name] will continuously monitor and oversee the procedure by checking vital signs. The patient may contact [name] for further questions/concerns.
  - b. In the event of an AE that occurs during the appointment, the facility is equipped with trained medical staff (physicians and nurses) who can respond quickly. Should an event occur, [name] and the nurses will be nearby to administer immediate medical care and send the patient to the nearest hospital. If the AE occurs after the appointment, the patient will be referred for prompt medical attention. The patient will be withdrawn from the study. [name] will monitor the patient until the problem has been resolved or has stabilized.
4. Consuming Ivabradine
- a. [name], a cardiologist, will give the patients specific instructions on the amount of ivabradine capsules they would need to consume each day. A research person will follow up with the patient the next day and once a week for the next 90 days to assess the patient's condition. The patient's conditions will be reported back to the PI. If the patients have reasons to believe that Ivabradine is causing any discomfort, consumption of the capsule will be stopped.
  - b. In the event of an AE that occurs during the appointment, the facility is equipped with trained medical staff (physicians and nurses) who can respond quickly. Should an event occur, [name] and the nurses will be nearby to administer immediate medical care and send the patient to the nearest hospital. If the AE occurs after the appointment, the patient will be referred for prompt medical attention. The patient will be withdrawn from the study. [name] will monitor the patient until the problem has been resolved or has stabilized.
5. Washout Period
- a. [name] will monitor the patients closely during this washout period. [name] will remove patients from the study if it is in their best medical interest. A research person will follow up with the patient once a week during this period to assess the patient's condition. The patient's conditions will be reported back to the PI.
  - b. If an AE occurs, the patient will be referred for prompt medical attention. The patient will be withdrawn from the study. [name] will monitor the patient until the problem has been resolved or has stabilized.

In the event that a patient either withdraws from the study or the investigator decides to discontinue a patient due to SAE, the patient will have appropriate follow-up medical monitoring. Monitoring will continue until the problem requiring hospitalization has resolved or stabilized with no further change expected, is clearly unrelated to study medication, or results in death.

#### **Plan for data management**

Data will be collected using standardized paper forms and will only be identified with the study's ID of the participant. The codes that link the name of the participant and the study ID will be kept confidential by the

Principal Investigator in a secured cabinet. Data will be entered in the computer independently by UCSD certificated and trained data entry staff, and discrepancies corrected by a supervisor based on source documents.

Data quality will be monitored by random inspection of the completed forms by the PI. If necessary, re-training of data collectors will be conducted.

